8.3. Safety Assessments

Planned timepoints for all safety assessments are provided in Table 3 and Table 4.

The investigator(s) and the sponsor will review the safety data.

Safety will be evaluated by monitoring all AEs and clinically significant abnormalities identified through physical examinations, vital signs, and laboratory assessments. Such events and laboratory and AE toxicities will be graded according to NCI CTCAE v5.0 (or higher). Laboratory safety assessments will include routine monitoring of hematology and blood chemistry and tests of immunologic parameters.

Adverse events, pregnancies, concomitant medications, procedures, and hospitalizations will be recorded from signing the ICF until 90 days after the last dose of treatment or until the start of new anticancer therapy, whichever occurs first. Participants who relapse or progress and/or

prematurely discontinue the study treatment will continue to be followed for SPM throughout the study.

Adverse events and concomitant medications terms will be coded using MedDRA and a validated medication dictionary.

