8.9.3. Survival Follow-Up/Completion of Study

All participants will be followed for survival status every 12 weeks (\pm 4 weeks) until death, lost to follow-up, withdrawal of consent for survival follow-up, completion of the 5-year follow-up interval, or the end of the study.

For participants who have entered the survival follow-up period, sites will continue to collect
data regarding initiation of new anticancer treatment
and report OS. For participants who do not intend to return to the
study investigator for their ongoing care, follow-up will be maintained by telephone contact,
patient records, and public records/databases at intervals of no longer than 12 weeks.

Additional survival assessments may be performed outside the 12-week interval if a survival update is required for an interim assessment to meet safety or regulatory needs.

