An important medical event is an event that may not result in death, be immediately life-threatening, or require hospitalization but may be considered serious when, based on appropriate medical judgment, the event may jeopardize the participant and may require medical or surgical intervention to prevent one of the outcomes listed in the above definition. Examples of such events include new invasive or malignant cancers (these would include secondary malignancies arising during the study that are distinct from the disease[s] under study), intensive treatment in an emergency department or at home for allergic bronchospasm, blood dyscrasias, or convulsions that do not result in hospitalization, or development of drug dependency or drug abuse, or suspected transmission of an infectious agent via a medicinal product. Secondary malignancies should always be considered SAEs.

For Japan, an event which may lead to disability is also considered as the important medical event. It includes a case that is exposed to a risk of dysfunction to an extent that interferes with daily life when the adverse drug reaction occurs. It does not include an adverse drug reaction that, had the reaction been more severe, may have caused disability.

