9.4. Reporting of Serious Adverse Events

Regardless of suspected causality (eg, relationship to study treatment or study procedure[s]), all SAEs occurring after the participant has signed the ICF through completion of the study *or* until the participant starts a new anticancer therapy (whichever occurs earlier) must be reported to the sponsor (or designee) within **24 hours** of learning of its occurrence, unless otherwise specified by the Protocol. The investigator will submit any updated SAE data to the sponsor (or designee) immediately, without undue delay but not later than within 24 hours of it being available. For Japan, this information must also be reported immediately to the head of the study site in Japan.

Investigators are not obligated to actively seek SAE information after the EOT visit. If the investigator learns of any SAE, including a death, at any time during this period, and he/she considers the event to be reasonably related to the study treatment or study participation, then the investigator must notify the sponsor (or designee) within 24 hours of becoming aware of the event.

After the initial AE/SAE report, the investigator is required to proactively follow each participant at subsequent visits/contacts. All SAEs and AESIs (as defined in Section 9.5.1) will be followed until resolution, stabilization, the event is otherwise explained, or the participant is lost to follow-up (as defined in Section 7.3).

Prompt notification by the investigator to the sponsor regarding an SAE is essential so that legal obligations and ethical responsibilities towards the safety of participants and the safety of a study treatment under clinical investigation are met.

If the SAE is not documented in the RSI of the IB or product information for study treatment (new occurrence) or marketed products, respectively, and is thought to be related to the study treatment, the sponsor or its designee may urgently require further information from the investigator for expedited reporting to health authorities. The sponsor or its designee may need to issue an Investigator Notification to inform all investigators involved in any study with the same drug that this SAE has been reported. SUSARs will be collected and reported to the competent authorities and relevant ethics committees in accordance with Directive 2001/20/EC or as per national regulatory requirements in participating countries.

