9.5.1. Adverse Events of Special Interest by eCRF

Adverse events of special interest are defined as a subset of ECIs that an investigator should urgently communicate information about the event to the sponsor/designee for further evaluation. Communication can be in the form of eCRF entry, email, or phone call to the sponsor/designee.

Adverse events of special interest for tafasitamab/placebo are TLS, IRRs and allergic reactions to study drug ≥ Grade 3, CRS, SPM, hepatitis B reactivation, and PML.

Adverse events of special interest for lenalidomide are second primary malignancy.

Adverse events of special interest will be captured in the eCRF and if any of the serious criteria is met, should be captured as an SAE as well.

Adverse events of special interest should be reported as a diagnosis and should include the symptoms of the event as 1 event term. For example, IRR with symptoms of hives, chills, and fever.

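### Section 8.3 does not name participants who complete treatment in remission for study-long follow-up of second primary malignancies, so late capture may depend on a post-randomisation outcome

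*Protocol*

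**What the plan says.** Protocol 8.3 states that adverse events "will be recorded from signing the ICF until 90 days after the last dose of treatment or until the start of new anticancer therapy", whichever is first. It then adds that participants who relapse or progress and/or "prematurely discontinue the study treatment will continue to be followed for SPM throughout the study". A participant who completes all 12 cycles without relapse or progression belongs to neither group.

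SPM matters to this plan. Protocol 9.5.1 lists it as an event of special interest for tafasitamab/placebo and adds: "Adverse events of special interest for lenalidomide are second primary malignancy". Section 9.2 says: "Secondary malignancies should always be considered SAEs".

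Section 9.4 pulls two ways. Its first paragraph requires reporting, whatever the causality, of "all SAEs occurring after the participant has signed the ICF through completion of the study", or until new anticancer therapy if earlier. Its second says: "Investigators are not obligated to actively seek SAE information after the EOT visit". It then requires notification of an SAE the investigator happens to learn of if "he/she considers the event to be reasonably related to the study treatment or study participation".

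Other contacts continue. Participants without progression keep scheduled scans (8.9.2), and "All participants will be followed for survival status every 12 weeks" (8.9.3). The visible adverse-event row of Table 3 ends at the 90-day safety visit.

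On analysis, SAP 8.2.1 limits AE summaries to treatment-emergent events, up to 90 days after the last dose; later events are only listed. SAP 8.1 plans no formal safety testing. The AESI tables in SAP Appendix A (3.2.31 to 3.2.34) are treatment-emergent tables.

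**The concern.** Participants who complete treatment in remission have the longest planned exposure to the two drugs for which SPM is an event of special interest, yet 8.3 leaves them out of study-long SPM follow-up. Someone who stops early in remission is in; someone who completes in remission is out until relapse. The protocol gives no reason for the difference.

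Membership of the unnamed group is decided after randomisation, and it depends on progression, which tafasitamab is meant to delay. If unsolicited reporting is less complete than active follow-up, late SPM capture could differ between arms for reasons unrelated to the true SPM rate. Events that were never collected cannot be restored at analysis.

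**Working it through.** **The plan's own figures.** The PFS assumptions come from Protocol 10.1, Table 12: medians 27.8 months (TGB) and 42.8 months (TGA), HR 0.65, 80% power, 2-sided 5%, 1:1.
- Freedman: (1.960 + 0.842)² × (1.65/0.35)² = 174.4 events. Schoenfeld: 4 × (1.960 + 0.842)² / (ln 0.65)² = 169.2. Both are within 3% of the stated 174.
- 27.8 / 0.65 = 42.8 months. 448 / 0.85 = 527.1, or 528 in equal arms.

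The medians are therefore consistent with the plan and are used below.

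**Progression-free at the end of treatment.** Twelve 28-day cycles last 336 / 30.4375 = 11.04 months. With exponential PFS, S(t) = 2^(−t/median):
- TGA: 2^(−11.04/42.8) = 83.6%
- TGB: 2^(−11.04/27.8) = 75.9%

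Early stopping for other reasons is not given for this trial. Two rates from the single-arm DLBCL study in Protocol 2.1.4.6 serve as assumed anchors: 12.3% stopped both drugs for adverse events, and 24.7% stopped one or both. At 12.3% in both arms, completers in remission are 0.836 × 0.877 = 73% and 0.759 × 0.877 = 67%.

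**Later person-time without solicited SPM follow-up.** Let f be the mean of S(t) from 90 days to 60 months after the end of treatment (months 14.0 to 71.0), multiplied by (1 − early stopping). With no early stopping, f is 52.0% (TGA) and 37.6% (TGB).

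**Apparent ratio when true SPM rates are equal.** Let q be the fraction of SPMs captured by unsolicited reporting, with full capture in the group named in 8.3. The apparent ratio is [1 − f_A(1 − q)] / [1 − f_B(1 − q)]. The documents give no value for q, so a range is shown. Deaths are ignored.

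| Early stopping TGA / TGB | Completers in remission TGA / TGB | f TGA / TGB | q = 0.8 | q = 0.5 | q = 0 |
|---|---|---|---|---|---|
| 0% / 0% | 83.6% / 75.9% | 52.0% / 37.6% | 0.97 | 0.91 | 0.77 |
| 12.3% / 12.3% | 73.3% / 66.6% | 45.6% / 33.0% | 0.97 | 0.92 | 0.81 |
| 24.7% / 24.7% | 63.0% / 57.2% | 39.2% / 28.3% | 0.98 | 0.94 | 0.85 |
| 24.7% / 12.3% | 63.0% / 66.6% | 39.2% / 33.0% | 0.99 | 0.96 | 0.91 |
| 40% / 15% | 50.2% / 64.5% | 31.2% / 32.0% | 1.00 | 1.01 | 1.01 |

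Example, second row at q = 0.5: (1 − 0.456 × 0.5) / (1 − 0.330 × 0.5) = 0.772 / 0.835 = 0.92.

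**Break-even.** With 12.3% stopping in TGB, the person-time shares are equal when stopping in TGA is 1 − (0.376 × 0.877) / 0.520 = 37%. With HR = 1 and equal stopping there is no differential. At q = 1 the ratio is 1.00 in every row.

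**Planned tables.** Up to 90 days after the last dose, 8.3 records adverse events under one rule for everyone, so this mechanism leaves the treatment-emergent SPM tables at a ratio of 1.00.

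**The case against.** The strongest reply is that a reader might infer that the trial's SPM comparison is biased in favour of tafasitamab, and the documents do not support that.

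- **No planned by-arm comparison is touched.** The AESI tables stop at 90 days after the last dose, where collection is equal. This stands in full.
- **Completers have some cover.** The first paragraph of 9.4 applies to everyone, and every SPM is an SAE. Sections 8.3 and 9.4 can be read as complementary: 9.4 until new therapy, 8.3 for those likely to leave 9.4's window. The Amendment 7 entry on 9.4 in Protocol Appendix J points to continued surveillance, though a change log shows intent only. This stands in part, because the second paragraph of 9.4 still removes any duty to ask and adds a relatedness test.
- **Capture could even be better in remission.** These participants keep scheduled imaging, while those who progress may be followed by telephone and records. This is fair, and it is why full capture in one group and half in the other is only an illustration. Imaging is still a poor substitute for asking: the SPMs in the earlier DLBCL study were basal cell carcinoma and myelodysplastic syndrome (Protocol 2.1.4.6).
- **Redaction.** Sections 8.2 and 8.9.3 have gaps where follow-up items are listed, so it cannot be said that no SPM item exists there. As visible, those sentences concern participants who have relapsed or progressed, or who have entered survival follow-up.
- **The effect is small against chance.** If the 3 of 81 participants with SPM in that study carried over to about 309 per arm, some 11 events per arm would give a 95% interval for the ratio of exp(±1.96 × √(2/11)), about 0.4 to 2.3. This stands as a limit on importance.

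**Conclusion.** The wording gap in 8.3 is real, and 9.4 does not clearly close it. Late SPM ascertainment may differ by a post-randomisation outcome. What is exposed is the set of SPMs recorded beyond 90 days after the last dose, now only listed, and any study-long SPM comparison made from them.

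The direction plausibly favours tafasitamab. That needs HR below 1, incomplete unsolicited capture, and early stopping in TGA that is not far above TGB. With 12.3% stopping in both arms and 50% capture, a true ratio of 1.0 would appear as about 0.92, and a true 1.5 as about 1.39 (1.5 × 0.924). Both the stopping rate and the capture rate are assumptions.

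Nor are completers in remission the majority throughout. They are at the end of treatment, but the progression-free share falls to 50% at 27.8 months in TGB and 42.8 months in TGA. This is a worthwhile and inexpensive correction to data collection. It does not call the planned safety tables into question.

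**What to change.** - **Protocol 8.3:** state that all participants are followed for SPM throughout the study, regardless of treatment completion, progression or new anticancer therapy.
- **Protocol 9.4:** exempt SPM from the sentence that removes the duty to seek SAEs after EOT, and from the relatedness condition that follows it.
- **Protocol Table 3 and eCRF:** add one SPM question to the existing 12-weekly survival contacts and the efficacy visits.
- **SAP 8.2 and Appendix A:** add a by-arm summary of all SPMs to the end of study, with exposure- or follow-up-adjusted rates, beside the treatment-emergent tables.

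With the same active follow-up for everyone, the differential from this cause disappears whatever the capture rate of unsolicited reporting. The cost is a reworded sentence, an exception, a schedule row with its eCRF question, slightly longer follow-up contacts and one added table. No treatment rule changes.

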8.3.1. Adverse Events

Adverse events that begin or worsen after informed consent should be recorded on the Adverse Events Form in the eCRF regardless of the assumption of a causal relationship with the study treatment. Conditions that were already present at the time of informed consent should be recorded on the Medical History Form in the eCRF. Adverse events (including laboratory abnormalities that constitute AEs) should be described using a diagnosis whenever possible rather than by individual underlying signs and symptoms.

Adverse events will be reported by the participant (or, when appropriate, by a caregiver, surrogate, or the participant's legally authorized representative). The investigator and any qualified designees are responsible for detecting, documenting, and recording events that meet the definition of an AE or SAE and remain responsible for following-up on AEs that are serious, considered related to the study treatment/procedures, or that caused the participant to discontinue the study treatment. Care will be taken not to introduce bias when detecting AEs and/or SAEs. Open-ended and nonleading verbal questioning of the participant, such as "How are you feeling?" is the preferred method to inquire about AE occurrences. Adverse events may also be detected when they are volunteered by the participant during the screening process or between visits or through physical examinations, laboratory tests, or other assessments. The definition, reporting, and recording requirements for AEs are described in Section 9.

All SAEs will be reported to the sponsor or designee within 24 hours. The investigator will submit any updated SAE data to the sponsor within 24 hours of it being available.

After the initial AE/SAE report, the investigator is required to proactively follow each participant at subsequent visits/contacts. All SAEs, nonserious AEs, and AESIs (as defined in Section 9.5.1), will be followed until resolution, stabilization, the event is otherwise explained, or the participant is lost to follow-up (as defined in Section 7.3).

8.3.2. Physical Examinations and Eastern Cooperative Oncology Group Performance Status

Physical examinations and ECOG performance status (see Appendix D) will be assessed according to the SoA (see Table 3).

A comprehensive physical examination will be performed by the investigator or a qualified designee during the screening and at EOT. Comprehensive physical examination should include at least cardiovascular, respiratory, abdominal, and neurologic assessment. The tumor assessment includes the evaluation of presence and degree of enlarged lymph nodes, liver, and spleen assessments.

Targeted physical examination will be guided by the individual participant's status and will include body systems associated with symptoms and/or the underlying FL/MZL disease (lymph node status, liver, spleen). Targeted physical examinations may be focused on tumor response assessment (eg, lymph nodes, liver, and spleen) and AEs per investigator discretion.

Body weight will be measured as indicated in the SoA (see Table 3) and height measured at screening only.

B-symptoms (fever, night sweat, weight loss) will be assessed at the timepoints indicated in the SoA (see Table 3).

8.3.3. Vital Signs

Vital signs include blood pressure, respiratory rate, pulse, and body temperature.

Vital signs should be measured at the timepoints described in the SoA (see Table 3). Vital signs should be obtained prior to the tafasitamab/placebo infusion, and then at least 3 times during the infusion (end of the infusion may be included as 1 of the 3 times), and/or as clinically indicated.

It is recommended that before vital signs are measured, the participant should be resting for approximately 5 minutes. If possible, vital sign assessments should be performed in the same manner at each timepoint.

8.3.4. Electrocardiograms, Echocardiograms, and/or Cardiac MUGA Scans

Standard 12-lead resting ECGs will be obtained at screening as described in the SoA (see Table 3). Electrocardiograms will be interpreted locally.

The investigator will evaluate the clinical significance of each ECG value outside the reference ranges (including QTc assessment), according to the nature and degree of the observed abnormality. Any new abnormal values or those deteriorating from baseline considered to be clinically significant should be reported as AEs.

If clinically significant abnormalities are observed or artifacts are present that result in an inability to adequately interpret the results, then the ECG will be repeated.

After study start, ECGs will be performed as clinically indicated as per local practices.

The decision to include or exclude a participant or discontinue study treatment based on an ECG flagged as "Abnormal, Clinically Significant" is the responsibility of the investigator, in consultation with the sponsor's medical monitor as appropriate. Clinically notable abnormalities that are considered clinically significant in the judgment of the investigator are to be reported as AEs.

Two-dimensional echocardiogram (2D-ECHO) or cardiac MUGA scan will be obtained at screening to evaluate cardiac function, including assessment of LVEF.

8.3.5. Laboratory Assessments

Any abnormal laboratory findings, regardless if centrally or locally analyzed, assessed by investigator as clinically significant will constitute an AE, and should be reported as such and followed until the outcome is known. Clinically significant abnormal laboratory findings are those that are not associated with the underlying disease, unless judged by the investigator to be more severe than expected for the participant's condition. All laboratory tests with values considered clinically significantly abnormal during participation in the study or within 90 days after the last dose of study treatment should be repeated until the values return to normal or baseline or are no longer considered clinically significant by the investigator or medical monitor.

Differences between central laboratory and local laboratory results may occur; central laboratory results will supersede local laboratory results.

Also, additional diagnostic tests may be indicated to determine a more precise diagnosis of the participant's condition (eg, ordering a WBC differential count to help characterize a high or low WBC count, or ordering a determination of RBC indices to help characterize a low hematocrit).

8.3.5.1. Central Laboratory Testing for Safety

The measurement of all safety laboratory parameters (except pregnancy testing) as indicated in this Protocol will be performed centrally. Central laboratory tests will be performed according to Table 4. Laboratory results are required for determining participant eligibility for study enrollment and will be used for the primary statistical analysis of the study results.

During screening, it is permitted to repeat the laboratory assessment of serum chemistry and hematology parameters due to the variability of the parameters and their dependence on multitude of factors (eg, hydration, muscle mass). This is valid provided no safety concerns arise and that such laboratory results might have been caused by a transient, medically plausible event, which resolved spontaneously or as result of a medical intervention in the meantime (eg, dehydration, vomiting, imaging procedure with a contrast). This procedure and the rationale behind it must be explicitly documented in source data. Such repeated assessment (once only) of the concerned parameters will not be counted as "rescreening" for that participant.

Laboratory samples may be taken as defined in Table 4. Local laboratory results may be used for taking treatment or clinically related decisions, or for the immediate safety management of a study participant; in that situation, the site will be requested to send a sample to the central laboratory for confirmation of the result(s). The investigator or designee should review laboratory results before dosing so that the administration of the study drug(s) may be adjusted or interrupted if necessary.

The laboratory results will be kept in the participant's source documentation. Any clinically significant discrepancies will be evaluated on a case-by-case basis. All blood samples will be processed and handled according to standard laboratory procedures. The time of blood collection should be documented in the source data.

Clinical laboratory parameters assessed in this clinical study are displayed in Table 11 below.

Table 11: Required Laboratory Analytes

Serum Chemistries	Hematology	Urinalysis
ALT	Hemoglobin	Glucose
Albumin	Hematocrit	Ketone
Alkaline phosphatase	Platelet count	Occult blood
Amylase	WBC count including differentials	pН
AST		Protein
Bicarbonate/CO ₂ (may not be	Coagulation parameters:	Specific gravity
applicable in Japan)	aPTT	Urobilinogen
Bilirubin (total, direct, indirect)	D-dimer	
Calcium	PT	
Chloride	TT	
CPK		
Creatinine	Immunological parameters:	
GGT	CRP	
Glucose		
Lactate dehydrogenase		
Phosphorous		
Potassium		
Protein (total)		
Sodium		
Blood urea nitrogen/urea		
Uric acid		

Note: Additional tests may be required, as agreed upon by the investigator and sponsor, based on emerging safety data or to rule out a diagnosis.

Note: Alternative tests (ie, CO₂ or CO₂ Combining Power or HCO₃) are also allowed as per regional standard of care.

IgA, IgG, IgM, and TSH assessments will be conducted as indicated in Table 4.

Urinalysis will be performed using a dipstick at screening and during study conduct as clinically indicated. A quantitative assessment may be required in the event of a positive or doubtful dipstick result.

